6.7.4. The Proportion of Participants With Normalization of Proteinuria

The proportion of participants with normalization of proteinuria (measured by triplicate FMU uPCR) at week 26 will be summarized using ITT set. The baseline and week 26 uPCR calculation will be handled the same way as in Section 6.5.1. Normalization of proteinuria is defined as test result values within the normal reference range.

A logistic model will be used to analyze the exploratory efficacy endpoint. The model will include treatment group as the independent variable and adjusted for baseline log-transformed uPCR values, disease type (C3G vs IC-MPGN), and stratification factors. Further details on the presentation of the results are described in Section 6.1. ICE strategies will be the same as those specified in Section 6.5.1.1.

A data listing for each participant's normalization status at week 26 be provided using ITT set.

6.7.5. Time to 50% Reduction in uPCR With a Stable or Improved eGFR

Time to 50% reduction in uPCR with a stable or improved eGFR (a.k.a., achieving the composite renal endpoint as defined in Section 6.5.1) will be summarized using ITT set with the Kaplan-Meier method (Kaplan and Meier 1958), using plots and presentation of median (and 95% CIs) for time-to-event. Participants who did not have the event at or prior to Week 26 in study will be censored at the minimum of the last date of contact or their treatment discontinuation date, or their Week 26 visit or first dose date+182 if Week 26 is missing. Participants who were randomized but did not receive any treatment will be censored at Day 1. Time to vent (or censor) will be calculated as date of event (or censor date) – Day 1 date +1. Event rates at week 12 and week 26 will also be presented in the summary tables. Comparisons between treatment groups will be done using Cox proportional hazard models (Cox 1976) stratified by disease type (C3G vs IC-MPGN) and stratification factors, and adjusted for baseline eGFR values and baseline log-transformed uPCR values. The hazard ratio, 95% CI, and p-value will be presented for the pegcetacoplan group over placebo group.

A data listing for each participant's time to achieve 50% reduction in uPCR with a stable or improved eGFR will be provided using ITT set.

6.7.6. Time to Normalization for Selected Parameters for Participants in Whom the Parameter is Abnormal at Baseline

For parameters serum C3, uPCR (measured by triplicate FMU), serum albumin, and blood pressure (both SBP and DBP), time to normalization (in weeks) will be summarized using ITT set with the Kaplan-Meier method, using plots and presentation of median (and 95% CIs) for time-to-event. Participants who did not have the event at or prior to Week 26 in study will be censored at the minimum of the last date of contact or their treatment discontinuation date, or their Week 26 visit or first dose date+182 if Week 26 is missing. Participants who were randomized but did not receive any treatment will be censored at Day 1. Time to vent (or censor) will be calculated as date of event (or censor date) – Day 1 date +1. Event rates at week 12 and week 26, as well as p-values from the log-rank test (stratified by disease type and stratification factors) will also be presented in the summary tables. The analyses will be based on participants whose test result being abnormal at baseline.

A data listing for each participant's time to normalization for these parameters will be provided using ITT set.

6.7.7. The Change From Baseline in Glomerular Macrophage Count

The observed values for glomerular macrophage count, determined by CD68 staining, will be summarized by treatment group and visit using ITT set. The categories for glomerular macrophage count are: 0 = None, 1 = Mild (<25% glomeruli), 2 = Moderate (26 to 50 % glomeruli), 3 = Severe (>50 – 75 % glomeruli), and 4 = Extensive (>75%).

All glomerular macrophage count results will be listed for the ITT set.

6.7.8. The Change From Baseline in PGIC Score

A shift table of changes in PGIC score from baseline to week 26 will be tabulated by treatment group.

All PGIC score results will be listed for the ITT set.

6.7.9. The Change From Baseline in EQ-5D-5L Score

The observed values for EQ-5D-5L score (based on visual analog scale) will be summarized by treatment group and visit using ITT set. Summaries will present the descriptive statistics for baseline, absolute values, change and percentage change from baseline data by visit.

An ANCOVA model will be used to analyze the exploratory endpoint. The model will include treatment as a fixed effect, adjusted for baseline EQ-5D-5L score, disease type (C3G vs IC-MPGN), and stratification factors. Further details on the presentation of the results are described in Section 6.1. No multiple imputations will be applied. ICE strategies will be simplified where participants with missing data at week 26 (whether due to ICE or not) will be excluded from the modeling. Alternative approaches on the construction of EQ-5D-5L score may be explored as post-hoc analysis if necessary.

All EQ-5D-5L score results will be listed for the ITT set.

6.7.10. The Change From Baseline in WPAI Score

The observed values for WPAI score will be summarized by treatment group and visit using ITT set. Summaries will present the descriptive statistics for baseline, absolute values, change and percentage change from baseline data by visit.

The WPAI score is constructed based on the responses to the 6 questions: Q1=currently employed, Q2=hours missed due to specified problem, Q3=hours missed other reasons, Q4=hours actually worked, Q5=degree problem affected productivity while working, Q6=degree problem affected regular activities. Each response will be multiplied by 100 to express in percentages. And the WPAI score is constructed as Q2/(Q2+Q4)+[(1-(Q2/(Q2+Q4)))x(Q5/10)], which indicates percent overall work impairment due to problem.

An ANCOVA model will be used to analyze the exploratory endpoint. The model will include treatment as a fixed effect, adjusted for baseline WPAI score, disease type (C3G vs IC-MPGN), and stratification factors. Further details on the presentation of the results are described in Section 6.1. No multiple imputations will be applied. ICE strategies will be simplified where participants with missing data at week 26 (whether due to ICE or not) will be excluded from the modeling.

All WPAI score results will be listed for the ITT set.

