6.7.21. The Change from Baseline in WPAI Score

The descriptive analysis described in Section 6.7.11 in the main SAP will be repeated at Week 52 based on the ITT Set by using available data through the Week 52 assessment.

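### Followed literally, the WPAI scoring rule in SAP 6.7.10 scales the responses instead of the result, so the score falls short of a percentage by 99 points times the fraction of hours missed

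*SAP*

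**What the plan says.** SAP 6.7.10 states that "The WPAI score is constructed based on the responses to the 6 questions" and lists the six items. Q2 is hours missed because of the health problem, Q4 is hours actually worked, and for Q5 the text reads "Q5=degree problem affected productivity while working". It then instructs: "Each response will be multiplied by 100 to express in percentages". The formula follows directly. With A = Q2/(Q2+Q4), it is A + (1 − A) × (Q5/10), "which indicates percent overall work impairment due to problem".

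The score is summarised by visit and analysed at week 26 by ANCOVA: "The model will include treatment as a fixed effect, adjusted for baseline WPAI score, disease type (C3G vs IC-MPGN), and stratification factors". For the open-label period, section 6.7.21 of the SAP addendum says that the descriptive analysis "will be repeated at Week 52 based on the ITT Set by using available data through the Week 52 assessment". It points to main SAP 6.7.11 for the method, but that section is the uPCR and eGFR correlation analysis; WPAI is 6.7.10.

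No other place gives a different scoring rule. Protocol 10.8.5 describes the questionnaire only. The sample code in SAP 17.2 has no WPAI derivation. The list of changes in addendum section 15 does not mention WPAI.

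**The concern.** The formula takes the responses as its inputs. An instruction to scale each response can therefore act only before or inside the formula, and nothing in the text says to multiply the result by 100. The factor does not pass through the formula evenly: it cancels in a ratio of hours but not in Q5/10. The two parts of the score are then added on different scales.

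At stake is whether a programmer, an independent second programmer or an outside reader who follows the text would obtain the percentage that the SAP names. If not, the error would carry into the listings, the by-visit summaries, the week 26 ANCOVA and the week 52 summaries. It would affect every participant who missed any hours because of the disease.

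**Working it through.** The documents state no numeric WPAI value, so there is no figure of the plan's own to reproduce. The check evaluates the formula in two ways.

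**Inputs**
- Scaling instruction, formula and declared unit: SAP 6.7.10.
- Range of Q5: not stated in SAP 6.7.10 or Protocol 10.8.5. I assume 0 to 10, inferred from the divisor 10.

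**Literal rule (each response × 100 first)**
- Hours ratio: 100·Q2/(100·Q2 + 100·Q4) = Q2/(Q2+Q4) = A, unchanged, between 0 and 1.
- Productivity term: 100·Q5/10 = 10·Q5, between 0 and 100.
- Literal score: A + (1 − A) × 10·Q5.

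**Coherent rule (raw responses, result × 100)**
- 100 × [A + (1 − A) × Q5/10] = 100·A + (1 − A) × 10·Q5.

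**Difference**
- Coherent minus literal = 100·A − A = 99·A, whatever the value of Q5. It is zero only when no hours were missed.

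**Cases**

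| Q2 (h missed) | Q4 (h worked) | Q5 | A | Literal | Coherent | 99·A |
|---|---|---|---|---|---|---|
| 5 | 35 | 3 | 0.125 | 0.125 + 0.875 × 30 = 26.375 | 12.5 + 26.25 = 38.75 | 12.375 |
| 20 | 20 | 3 | 0.5 | 0.5 + 0.5 × 30 = 15.5 | 50 + 15 = 65 | 49.5 |
| 38 | 2 | 0 | 0.95 | 0.95 + 0 = 0.95 | 95 + 0 = 95 | 94.05 |

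**Direction**
- The literal score changes with A at rate 1 − 10·Q5. For Q5 of 1 or more this is at most −9, so the score falls as missed work rises with Q5 held fixed.
- At Q5 = 0 the rate is +1: the score is compressed to 0 to 1 but not reversed.
- The coherent score changes at rate 100 − 10·Q5, which is never negative for Q5 up to 10.
- At Q5 = 5, as A goes 0, 0.5, 0.9, 0.975, the literal score goes 50, 25.5, 5.9, 2.2. The coherent score goes 50, 75, 95, 98.75.

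**Effect on a change score**
- Suppose a participant moves from the second row of the table to the first: 15 fewer hours missed, Q5 still 3. The coherent change is 38.75 − 65 = −26.25, an improvement. The literal change is 26.375 − 15.5 = +10.875, a worsening.
- If Q5 also drops to 1, the final literal score is 0.125 + 0.875 × 10 = 8.875 and the change is 8.875 − 15.5 = −6.625, an improvement. The coherent final score is 12.5 + 8.75 = 21.25, a change of −43.75. The sign is now right, but the size is far too small.

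**Another reading**
- The instruction might be meant for the two components, with each percentage then entered in the formula. For Q2 = 20, Q4 = 20, Q5 = 5 that gives 50 + (1 − 50) × 50 = −2400, so this reading also fails.

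**The case against.** The strongest reply is that SAP 6.7.10 itself makes the literal reading unlikely. The variables are defined in raw units, and the formula is correct on raw inputs. The divisor 10 makes sense only if Q5 is unscaled. The stated purpose is a percentage, and multiplying hours or employment status by 100 does not produce one. An analyst who knows the instrument would scale the result and obtain the right score. This largely stands: the sentence is probably loose wording.

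It follows that two stronger inferences are not supported. A reader might conclude that the reported WPAI results are wrong. The documents show no WPAI code, so they cannot establish how the score was programmed. A reader might also conclude that a treatment returning people to work would appear to worsen WPAI. That needs literal programming, Q5 of at least 1, and Q5 not falling enough as hours recover to offset the reversal; at Q5 = 0 there is no reversal at all.

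The reply is also right that little depends on this endpoint. WPAI is exploratory (SAP 2.2.4) and outside the fixed testing sequence (SAP 6.2). The addendum specifies no formal testing of open-label data (addendum 6.2).

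What the reply does not remove is that the instruction gives a wrong score when followed, and no other section corrects it. The revision history of SAP 2.0 lists added detail on the WPAI analysis, so this section is the place where a reader would look for the scoring rule.

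**Conclusion.** The scoring rule is wrong as written. Executed literally, it understates the percent score by 99 × A points, which is 12.4, 49.5 and 94.1 points in the three cases tabulated. With Q5 fixed at 1 or more, it also ranks participants with more missed work as less impaired. The 99 × A shortfall is algebraic and does not depend on the range of Q5. The 0 to 100 span of the productivity term does, and rests on the assumed 0 to 10 rating.

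This is an error of specification. Whether any result is affected depends on how the derivation was programmed, which the documents do not show. No primary or secondary conclusion is touched.

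**What to change.** Replace the scaling sentence in SAP 6.7.10 with:

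> The WPAI score is computed from the raw responses (hours for Q2 and Q4, the 0-10 rating for Q5), and the resulting score is multiplied by 100 to express it as a percentage.

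This also puts the Q5 range on record; confirm it against the questionnaire used. Then check that the derivation code matches for the week 26 ANCOVA and the week 52 summaries, and point addendum 6.7.21 to main SAP 6.7.10.

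The cost is one sentence, a corrected cross-reference and a code check. If the variable was programmed literally, it must be re-derived and the WPAI outputs rerun, which is a small programming task. No new data are needed.

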6. INVESTIGATIONAL PLAN

This phase 3 randomized, placebo-controlled, double-blinded, multicenter clinical study is designed to evaluate the safety and efficacy of twice-weekly SC infusions of pegcetacoplan in patients with primary C3G or IC-MPGN. There will be approximately 80 to 100 participants enrolled in this study, at least 78 of whom will have native kidney disease and up to 22 of whom may have posttransplant recurrence of C3G or IC-MPGN. At least 63 participants with C3G in native kidney will be enrolled. The enrollment of participants with C3G or IC-MPGN will be monitored to ensure balance between the groups. At least 10 adolescent participants (aged 12-17 years) will be enrolled; adolescent participants may be either patients with native kidney disease or posttransplant disease recurrence. Participants initially screened as adolescents will follow adolescent procedures and requirements through the duration of their participation in study, even if they pass their 18th birthday while enrolled in the study.

The planned length of participation in the study for each participant is a maximum of approximately 70 weeks. This study will consist of 4 parts:

- Part 1: 10-week screening period
- Part 2: 26-week randomized controlled period (RCP)
- Part 3: 26-week open-label period
- Part 4: 8-week follow-up period (only for participants who do not roll into a long-term extension study)

Informed consent (and assent, when applicable) will be obtained prior to any study-related procedures being conducted. The screening period will start once informed consent has been obtained.

See Figure 1 for the study schematic, and Table 2 for the schedule of activities.

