10.8.5. Work Productivity and Activity Impairment Questionnaire: Specific Health Problem

The Work Productivity and Activity Impairment Questionnaire: Specific Health Problem (WPAI:SHP) is a patient-reported quantitative assessment of the amount of absenteeism, presenteeism, and daily activity impairment attributable to a specific health problem for working patients. It includes 6 questions assessing health-related work productivity loss over the previous 7 days.

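### The WPAI analysis compares only participants with work hours at both visits, drops anyone who leaves work, and leaves the collected daily-activity item unscored

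*SAP*

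**What the plan says.** SAP 6.7.10 lists six items: "Q1=currently employed, Q2=hours missed due to specified problem, Q3=hours missed other reasons, Q4=hours actually worked", then Q5 (productivity while at work) and "Q6=degree problem affected regular activities". It defines one score. With A = Q2/(Q2+Q4), the score is A + (1-A) x Q5/10, the quantity "which indicates percent overall work impairment due to problem". Q1, Q3 and Q6 do not enter it.

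The week 26 analysis is an ANCOVA adjusted for the baseline WPAI score. No multiple imputation is applied, and "participants with missing data at week 26 (whether due to ICE or not) will be excluded from the modeling". The section has no rule for a participant who answers no to Q1 or reports no hours. Descriptive summaries and listings use the ITT set.

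Protocol 10.8.5 says the instrument measures absenteeism, presenteeism and "daily activity impairment attributable to a specific health problem for working patients". The Schedule of Activities places WPAI in the quality-of-life battery at screening visit 2, week 26 and week 52, without an age or employment limit. Protocol Section 6 states: "At least 10 adolescent participants (aged 12-17 years) will be enrolled". Addendum 6.7.21 repeats the WPAI analysis descriptively at week 52 and adds no score from Q6. WPAI is an exploratory endpoint in both documents.

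**The concern.** The score exists only for people with work hours, and the ANCOVA needs it at both baseline and week 26. Participants without a job at baseline never enter the model. Those who lose or leave their job during treatment fall out at week 26.

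The second group matters more. Being employed at week 26 can be affected by treatment and by disease course, so restricting to it gives up the protection of randomization. A participant who gives up work because of C3G or IC-MPGN has a poor work outcome, yet the rule treats that person as missing. At stake is whether a reported WPAI difference describes the randomized arms or only those who kept working. The item whose wording does not depend on having a job, Q6, is collected and not scored.

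**Working it through.** The plan gives no sample size, power or expected effect for WPAI, so there is no figure of its own to reproduce. The check has three parts.

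**1. The formula by employment state** (A = Q2/(Q2+Q4); score = A + (1-A) x Q5/10)

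- Employed, Q2=0, Q4=40, Q5=3: A = 0, score = 0.30, or 30%.
- Employed, Q2=10, Q4=30, Q5=4: A = 0.25, score = 0.25 + 0.75 x 0.4 = 0.55, or 55%.
- Employed but absent all week because of the disease, Q2=40, Q4=0: A = 1, score = 100% whatever Q5 is, but missing if Q5 is blank.
- Employed, Q2=0 and Q4=0 (for instance a week off for other reasons): 0/0, undefined.
- Not employed, Q2 to Q5 blank: missing. Not employed, zeros entered: 0/0, undefined.
- Changing Q6 never changes the score.

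So a participant employed at baseline who has left work by week 26 has no week 26 score and leaves the ANCOVA.

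**2. How many could be scored**

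Final enrollment was 124 (protocol amendment summary). Employment is not given. Assume 30% to 70% are employed at baseline and 80% to 100% of those still are at week 26:

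- low: 124 x 0.30 x 0.80 = 29.8, about 30
- high: 124 x 0.70 x 1.00 = 86.8, about 87

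The difference in the work score detectable with 80% power (two-sided 5%, equal arms) is (1.96 + 0.84) x 2/sqrt(n) SD: about 1.03 SD at the low end and 0.60 SD at the high end.

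**3. What selection on employment can do**

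Assumptions, none from the documents: scores normal with SD 20 points, higher is worse, true active-minus-placebo difference -8, and the worst-scoring share p of an arm leaves work. Removing the top share p lowers the arm mean by 20 x phi(z)/(1-p), where z is the 1-p normal quantile:

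| p | z | phi(z) | shift (points) |
|---|---|---|---|
| 3% | 1.881 | 0.0680 | 1.40 |
| 5% | 1.645 | 0.1031 | 2.17 |
| 10% | 1.282 | 0.1755 | 3.90 |
| 15% | 1.036 | 0.2332 | 5.49 |

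The scored difference is -8 minus the active shift plus the placebo shift:

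- placebo 10%, active 3%: -8 - 1.40 + 3.90 = -5.5
- placebo 15%, active 5%: -8 - 2.17 + 5.49 = -4.7
- 10% in both arms: -8 - 3.90 + 3.90 = -8
- placebo 3%, active 10%: -8 - 3.90 + 1.40 = -10.5

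The same rule can shrink, preserve or enlarge the difference.

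**The case against.** The strongest defence is that this is a choice of construct. Protocol 10.8.5 describes the instrument as being for working patients, and an overall work-impairment score has meaning only for workers. The SAP states the exclusion openly. Activity limitation is also partly covered elsewhere: EQ-5D-5L has a usual-activities dimension, and Addendum 6.7.20 tabulates its components for the randomized period too. WPAI is exploratory and outside the fixed-sequence tests. All of this stands and limits the weight of the point. It does not supply a rule for participants without work hours, and it does not remove the conditioning on week 26 employment.

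Several stronger readings are tempting, and the documents do not support them:

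- **That the selection hides a benefit.** This needs more leavers on placebo. Equal rates leave the difference unchanged in the illustration above, and reversed rates exaggerate it.
- **That adolescents cannot be scored.** One with paid work can be.
- **That anyone who stops attending work is lost.** A participant still employed but absent all week scores 100% if Q5 is answered.
- **That every participant can answer Q6.** This is inferred from the item's wording and the unrestricted schedule, and the phrase about working patients in Protocol 10.8.5 pulls the other way.
- **That the square root of enrolled over scorable N measures precision lost against Q6.** The two scores are different constructs with their own SDs and effects.
- **That the work score should be replaced.** It is prespecified, and demoting it would be a trade-off, not a correction.

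**Conclusion.** The point holds in a limited form. As written, the week 26 WPAI model is a complete-case comparison of participants with work hours at baseline and week 26. Those who leave employment are removed and not counted as impaired, and Q6 enters no score in the SAP or the addendum. That participants without a job drop out follows from the formula together with the exclusion rule; the SAP does not say it outright.

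The comparison can be biased in either direction. The numbers scored and the size of any bias rest entirely on assumed employment shares, leaving rates and SD. The primary and secondary results are untouched. This is a cheap repair to an exploratory analysis, worth making so that a reported WPAI difference is not read as covering all randomized participants.

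**What to change.** In SAP 6.7.10:

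- Keep the prespecified work-impairment score. State that it applies to participants employed with nonzero hours (Q2+Q4 > 0) at both visits, and report that N per arm.
- Add activity impairment, Q6/10 x 100%, as a second WPAI score, using the same week 26 ANCOVA in all participants who answer Q6.
- Tabulate employment status (Q1) by arm and visit, so that differential leaving can be seen.

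In Addendum 6.7.21, add the Q6 score and employment status as descriptive summaries only. That section is descriptive, and no formal testing is planned on open-label data. Its cross-reference also needs correcting: it points to main SAP 6.7.11, the correlation analysis, where 6.7.10 is meant.

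The data are already scheduled for collection, so the cost is wording, one table and one extra exploratory model. The addendum records that week 26 results were reported in December 2024; if the Q6 model is added after unblinding, label it post hoc.
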